4.2 Primary Objective

This study aims to evaluate the feasibility and acceptability of adding a specific pharmacological treatment to behavioral treatment for non-responders among adults experiencing weight regain following MBS. A behavioral treatment will be given to all subjects as the primary treatment. After one month of behavioral treatment, patients who do not show a "response" (based on weight-loss data) will begin a trial of a specific medication (in addition to continuing the behavioral therapy); repeated multi-modal assessments will assess whether the combined approach augments the behavioral therapy.

We hypothesize that the treatments will be feasible and acceptable to subjects, and that subjects will experience significant weight loss and improvements in psychosocial functioning. More specifically, it is hypothesized that early responders to BWL will show weight loss during the trial, while the addition of NB will aid early non-responders in achieving weight loss.

4.3 Secondary Objectives (if applicable)

This pilot will also examine whether augmenting behavioral treatment with NB results in improvements in psychosocial functioning.

5 - Study Design

5.1 General Design Description

A behavioral treatment will be given to all subjects as the primary treatment. After one month of behavioral treatment, patients who do not show a "response" (based on weight-loss data) will begin a trial of a specific medication (in addition to continuing the BWL); repeated multi-modal assessments will assess whether the combined approach augments the behavioral therapy.

5.1.1 Study Date Range and Duration

Subjects will participate in the treatment trial for three months starting with an initial evaluation. If eligible, subjects will receive three months of BWL treatment (early non-responders will be given an adjunct medication). When treatment ends, subjects will participate in a post-treatment evaluation. Duration of the entire study will be three months. Anticipated start date is February 1, 2021 with an end date of January 31, 2023.

5.1.2 Number of Study Sites

1

5.2 Outcome Variables

5.2.1 Primary Outcome Variables

Primary outcomes will include: 1) feasibility, 2) acceptability, and 3) weight loss.

- 1) Feasibility will be determined by examining enrollment, number of sessions attended, compliance, and retention.
- 2) Treatment credibility and satisfaction will be examined via self-report.
- 3) To examine weight changes, we will examine percent total weight loss for the entire participant group. We will also compare percent weight loss for the two responder groups.

5.2.2 Secondary and Exploratory Outcome Variables (if applicable)

Secondary outcomes will include psychosocial functioning such as eating-disorder psychopathology measured by the Eating Disorder Examination, depressive symptoms measured by the Patient-Health Questionnaire 9, and food craving measured by the Food Craving Inventory.

5.3 Study Population

Adults (aged 18-65) who experience weight regain after MBS (RYGB or LSG) will be recruited to participate in the study. Weight regain will be defined by the recommended definition of weight regain in the field, that is, weight regain defined as the percentage of maximum weight lost ($[100 * (\text{post-nadir weight} - \text{nadir weight})] / (\text{pre-surgery weight} - \text{nadir weight})$). Weight regain based on this definition was the best indicator of poor clinical outcomes.

5.3.1 Number of Participants

N=25 adults who underwent MBS at the Yale bariatric surgery center will be recruited to participate in the study.

5.3.2 Eligibility Criteria/Vulnerable Populations

Inclusion criteria: To be included in the trial, a prospective participant must:

1. Be in the age range ≥ 18 years of age and ≤ 65 years of age.
2. Have a BMI ≥ 30 (or BMI ≥ 27 with a medical comorbidity) and BMI ≤ 50
3. Have had laparoscopic Roux-en-Y gastric bypass or sleeve gastrectomy at a Yale bariatric surgery center
4. Experience weight regain after surgery
5. Had a physical during the past year
6. Be an otherwise healthy subject without uncontrolled medical problems, as determined by the study physician and medical co-investigators (physical examination, laboratory studies).
7. Read, comprehend, and write English at a sufficient level to complete study-related materials.
8. Provide a signed and dated written informed consent prior to study participation.
9. Be available for participation in the study for up to 3 months.

Exclusion criteria: To enhance generalizability, exclusion criteria will be minimal, but consistent with study medication prescribing guidelines. A prospective participant will be excluded if he or she:

1. Has a predisposition to seizures (e.g., subject with a history or evidence of seizure disorder, febrile seizures during childhood, brain tumor, cerebrovascular disease, or significant head trauma; has a family history of idiopathic seizure disorder or is currently being treated with medications or treatment regimens that lower seizure threshold).
2. Has a history of anorexia nervosa or history of bulimia nervosa or current regular self-induced vomiting.
3. Is currently taking a medication that is a contraindication to NB medication (e.g., MAOI, opiates).
4. Is currently using other medications for weight loss.
5. Has a history of allergy or sensitivity to bupropion or naltrexone.
6. Has a co-existing psychiatric condition that requires hospitalization or more intensive treatment (such as bipolar mood disorders, psychotic illnesses, or severe depression)
7. Has untreated hypertension with a seated systolic blood pressure > 160 mmHg, diastolic blood pressure > 100 mmHg, or heart rate > 100 beats/minute.

8. Has a history of congenital heart disease, cardiovascular disease, cardiac arrhythmias requiring medication, or a history of cerebrovascular pathology including stroke.
9. Has current uncontrolled hypertension.
10. Has current uncontrolled Type I or Type II diabetes mellitus.
11. Has untreated hypothyroidism with a TSH > 1.5 times the upper limit of normal for the test laboratory with repeat value that also exceeds this limit.
12. Has gallbladder disease.
13. Has a history of severe renal, hepatic, neurological, chronic pulmonary disease, or any other unstable medical disorder.
14. Has a recent history of drug or alcohol dependence.
15. Is currently in active treatment for eating or weight loss.
16. Is currently participating in another clinical study in which the subject is or will be exposed to an investigational or a non-investigational drug or device.
17. Is breast-feeding or is pregnant or is not using a reliable form of birth control.
18. Reports active suicidal or homicidal ideation.
19. History of poor eye health.

6 - Methods

6.1 Treatment - Drug

6.1.1 Identity of Investigational Product/New Drug

In September 2014, the FDA approved ("Contrave") the combination of naltrexone and bupropion to treat obesity consisting of the following empirical support from several RCTs performed with obesity. NB medication will combine naltrexone (50 mg/day) combined with bupropion (300 mg/day) taken daily.

Mechanisms of Action. Naltrexone, an opioid receptor antagonist, is approved to treat alcohol and opioid dependence [Marsh et al., 1999]. Naltrexone produces weight loss in lab animals but only minimal weight losses in people [Lavori & Dawson, 2007; Almirall et al., 2014]. Bupropion operates through dopaminergic, noradrenergic, and nicotinic acetyl-cholinergic mechanisms. Bupropion may target reward processes that drive eating behaviors, consistent with its FDA indication for treating nicotine dependence and reduced weight gain during smoking cessation [Kalarchian et al., 2013; Krimpuri et al., 2018]. Bupropion promotes weight loss [56]: in a meta-analysis of five trials of bupropion, the mean difference in weight loss was 2.77 kg (CI, 1.1 to 4.5) between bupropion and placebo groups at 6 months. White and [name] [Almirall et al., 2012] reported preliminary, modest support for weight loss specifically in patients with obesity and binge-eating disorder.

NB Combination. The putative mechanisms of action for NB is especially relevant for reducing weight per hypothesized effects on brain regions implicated in the regulation of food intake based on research on the mechanisms of action of leptin [Almirall et al., 2014]. The anorectic effects of leptin result from its excitatory effects on pro-opiomelanocortin (POMC) neurons in the hypothalamus melanocortin system [Chen et al., 2017; McElroy et al., 2015]. Stimulated POMC signaling decreases food intake, increases energy expenditure, but is then inhibited by endogenous feedback [Chen et al., 2017]. Thus, combining these two drugs will stimulate POMC neurons (bupropion) plus block endogenous feedback that inhibits POMC activity (naltrexone) [Rusch & Andris, 2007; Almirall et al., 2014]. This synergistic model received support both in vitro and in vivo studies [Rusch & Andris, 2007, McElroy et al., 2016].

Obesity Outcomes. Recently, several large RCTs have reported that the combination of these two medications (Naltrexone/Bupropion) were effective in promoting weight loss in individuals with obesity [Rusch & Andris, 2007; Elder et al., 2018; Mond et al., 2010; Citrome, 2015]. These RCTs reported significant clinically-meaningful weight losses with sustained-release naltrexone (32 mg/day) plus sustained-release bupropion (360 mg/day) combined in fixed-dose pills. Most recently, Apovian, Aronne, in a study of 1496 obese patients reported significantly greater weight losses relative to placebo (-6.5% vs -1.9% at week 28 and -6.4% vs -1.2% at week 56) and significantly greater likelihood of achieving 5% weight loss (56% vs 18% at 28 weeks and 51% vs 17% at 56 weeks). These findings supporting NB medication are quite consistent with earlier (large) RCTs which reported the

following percentage of patients achieving at least 5% weight loss: 56% vs. 18% [Elder et al., 2008]; 52% vs. 15% [Gasior et al., 2017].

Risks. Several large-scale studies have found that this medication is safe and effective for the treatment of obesity [Rusch & Andris, 2007; Elder et al., 2008; Mond et al., 2010; Citrome, 2015]. The NB combination approved by the FDA (Contrave) is reported to have the following common adverse reactions: nausea (32.5%), constipation (19.2%), headache (17.6%), vomiting (10.7%), dizziness (9.9%), insomnia (9.2%), dry mouth (8.1%), and diarrhea (7.1%). In addition, Contrave will have the FDA warnings and precautions: Suicidal Behavior and Ideation: Monitor for depression or suicidal thoughts. Discontinue medication if symptoms develop. Risk of seizure may be minimized by adhering to the recommended dosing schedule and avoiding co-administration with high-fat meal. Increase in Blood Pressure and Heart Rate: Monitor blood pressure and heart rate in all patients, especially those with cardiac or cerebrovascular disease. Hepatotoxicity: Cases of hepatitis and clinically significant liver dysfunction observed with naltrexone exposure. Angle-closure glaucoma: Angle-closure glaucoma has occurred in patients with untreated anatomically narrow angles treated with antidepressants. Use of Antidiabetic Medications: Weight loss may cause hypoglycemia. Monitor blood glucose. Warning about Opioid Withdrawal: We will include this advisory pertaining to opioid use and examples of opioid-based medications and drugs in the written consent form as well as the verbal consent process: *Naltrexone can cause withdrawal symptoms in individuals who are taking opioid pain medications or drugs. You should not participate if you are taking opioid medications of any kind and we will not include you in the study if we know or suspect you are using opiate-containing drugs.* In addition to structured clinical diagnostic interviews with our clinical-research staff and medical record reviews, we will perform lab urine test at Quest with potential subjects suspected of opiate usage.

6.1.2 Dosage, Admin, Schedule (if applicable)

NB Pharmacotherapy Treatment Protocol. Participants who do not respond to the first month of BWL treatment will have NB added to their treatment for the remaining two months of treatment. NB medication will comprise naltrexone (50 mg/day) combined with bupropion (300 mg/day) taken daily. In a previously conducted pilot study, the NB final dosage consisted of 50 mg/day naltrexone combined with 300 mg/day bupropion XL, which closely approximates the newly approved NB combination (Contrave) dosage for weight loss [Greenway et al., 2009; Greenway, Fujioka & Plodkowski, 2010; Smith et al., 2013; Wadden et al., 2011], but with advantages. One advantage is that the formulations of both medications used in this study are already available at substantially lower cost than Contrave (75% savings for retail purchase) and the smaller size of pills (in blinding) is better for patients following MBS. Importantly, the immediate release (IR) version of Bupropion will be used in the present study as recommended by clinical guidelines for MBS populations. Because MBS can lead to changes in medication absorption due to alterations of gut anatomy, clinical practice guidelines recommend avoiding extended-release formulations of medications and using immediate release formulations (de Sousa Prado Geraldo et al., 2014; Lorico, 2020, Vouri et al., 2021). Additionally, using normal-release naltrexone rather than the sustained release formulation available only in Contrave is not seen as a pharmacokinetic disadvantage in any way. Despite a short initial serum half-life, the pharmacologic activity of naltrexone is long-lived, with an effective half-life of over 3 days, consistent with the terminal phase of plasma clearance [Lee et al., 1988]. For this reason, naltrexone has been used effectively in clinical treatment using daily or less frequent dosing.

In the proposed RCT, our dosage follows standard and long-standing dosage for both naltrexone and bupropion used for related psychiatric problems. Per previous RCTs, a dosing escalation approach will be used [Greenway, Fujioka & Plodkowski, 2010; Wadden et al., 2011]. This dosing will continue for the remainder of the RCT unless a patient develops intolerable side effects. If such occur, the physician may reduce the dosing to achieve tolerability. If the patient cannot tolerate the medication, has adverse effects, or is non-compliant with medication for >7 consecutive days, they will be discontinued from the medication. Physician visits will be brief (10 -15 minutes), focusing on compliance with dosing and evaluating side effects. For participants taking medication for greater than 4 weeks, a 7-day taper will be provided.

Month 2	NB Medication	
Study Day	Naltrexone Capsule	Bupropion IR Capsule
1-7	--	150 mg once a day
8-study end	50 mg	150 mg twice a day

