3.3.1 Potential Risks

The primary risks of this study are the BWL therapy, the pharmacologic therapy with NB, the assessment procedures, and lack of efficacy.

BWL: BWL is an established and widely-used intervention for obesity. The only foreseeable risks include some mild discomfort or embarrassment when discussing eating patterns or body image concerns. Previous controlled clinical trials with similar interventions with large numbers of similar patients have not reported problems. Any troublesome effects would be readily identifiable by the experienced research clinicians during the repeated evaluations. Thus, the risks of BWL are judged to be minimal.

NB: NB combination is FDA-approved for the treatment of obesity. Both medications will be used in the present study. NB has demonstrated safety, tolerability, and efficacy for patients with obesity treated over much longer periods of time (>12 months) than in the present study (Greenway et al., 2010). NB was associated with the following side effects in 10% or more of the time and significantly greater than rate in placebo: nausea, headache, constipation, and vomiting. NB was associated with the following side effects less than 10% of cases but significantly more than placebo: dizziness, insomnia, dry mouth, and diarrhea. Less common side effects include risk of seizure, increase in blood pressure and heart rate, hepatotoxicity, and angle-closure glaucoma. Large studies (e.g., Greenway et al., 2010 with N=1742) reported that the proportion of participants reporting a serious adverse event did not differ between NB and placebo (1.6% versus 1.4%) and none of the observed events

were judged to be related to the study. In keeping with the FDA advisory pertaining to antidepressants, including bupropion, the following information will be included in the study consent forms:

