"The U.S. Food and Drug Administration (FDA) has issued an Advisory cautioning health care providers, patients, and families to closely watch individuals taking bupropion for signs of their depression getting worse and for thoughts of killing or harming themselves, especially during the first several weeks that bupropion is being taken. Patients and their families should watch for and promptly report new symptoms. For example, report to the study doctor as soon as possible any signs of impulsivity (taking action or saying something without thinking first), agitation (feeling nervous or finding sitting still very difficult), and panic attacks (extreme fear without apparent reason)."

To monitor changes in depressive symptoms, patients will be asked to complete the PHQ-9 at monthly clinic visits. The research clinicians, who are trained and supervised by licensed psychologists in suicidal assessment, will review PHQ-9s during the clinic visit, and will ask pointed questions pertaining to suicidality/suicidal ideation (i.e., suicidal thoughts, plan, means, and intent) using the Columbia Suicide Severity Rating Scale. If it appears, based on the clinical judgment of the research clinician, that the participant is experiencing significant adverse effects of the medication, the investigators and study physician will be consulted and a determination of whether to discontinue the medication will be made. If warranted, the participant will be given a referral and safety planning will be implemented. If any participant experiences adverse reactions, or if side effects are too severe, the medication will be discontinued.

Assessments: Completion of the assessment procedures may cause some mild anxiety or embarrassment to some patients. Drawing blood from a vein to perform necessary laboratory tests is quite safe. Sometimes a bruise will occur at the puncture site and on very rare occasions a blood clot or infection may occur. If this occurs, appropriate treatment will be instituted immediately.

Failure to Improve: There is a chance that the patients will not lose weight or will gain weight during the study. Patients will be withdrawn from the study if their clinical condition deteriorates to a significant degree. Our experience with numerous RCTs is that this is quite rare.

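### Section 6.1.2 offers dose reduction for intolerable side effects, then requires stopping NB for adverse effects of any severity; section 3.3.1 has a similar unqualified trigger

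*Combined protocol and SAP*

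**What the plan says.** Section 6.1.2 sets the NB dose and what to do when a patient does not tolerate it. Three consecutive sentences matter:

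- Default: "This dosing will continue for the remainder of the RCT unless a patient develops intolerable side effects".
- Reduction: "If such occur, the physician may reduce the dosing to achieve tolerability".
- Stop: "If the patient cannot tolerate the medication, has adverse effects, or is non-compliant with medication for >7 consecutive days, they will be discontinued" (the sentence ends by making clear that it is the medication that stops).

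The same section describes short physician visits "focusing on compliance with dosing and evaluating side effects".

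Section 3.3.1 covers the same ground in its paragraph on monitoring depression and suicidality. If the research clinician judges that there are "significant adverse effects of the medication, the investigators and study physician will be consulted and a determination of whether to discontinue the medication" is made. The paragraph then closes: "If any participant experiences adverse reactions, or if side effects are too severe, the medication will be discontinued".

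Three other places bear on the rule. Section 6.2 collects adverse events at clinic visits with a checklist of the events most often reported for NB. Section 7.12 grades severity from mild to fatal in five steps. Section 6.1.1 (Risks) directs stopping the drug if suicidality emerges, and section 6.2.2 directs it for pregnancy.

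**The concern.** In section 6.1.2 the stop is mandatory, its triggers are alternatives, and one of them is simply having adverse effects. That trigger is wide enough to take in everything the reduction sentence was written for, and also the mild effects that the default sentence says should not interrupt dosing. A clinician facing tolerable nausea can find support in one section both for continuing and for stopping.

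This matters because the primary objective (section 4.2) is whether adding NB for non-responders is feasible and acceptable, and compliance is one of the named feasibility measures (section 5.2.1). Clinicians who follow the literal rule will withdraw NB from patients who tolerate it, and exposure will fall below the section 6.1.2 schedule. The 95% confidence interval for weight loss in the non-responder arm (section 6.4.1) would then describe NB stopped at the first adverse effect. Under the graded reading it would describe NB with dose adjustment. A later trial planned from these data needs to know which regimen was tested.

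**Working it through.** The plan gives no figure on this point, so the check compares the rules.

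**Step 1. Triggers and actions in section 6.1.2.**

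- Reduction rule: trigger, intolerable side effects; action, permissive.
- Stop rule: trigger, cannot tolerate, or has adverse effects, or non-compliant for more than 7 consecutive days; action, mandatory.

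**Step 2. Are the triggers nested?** In ordinary usage an intolerable side effect is an adverse effect. Every patient who meets the reduction trigger therefore also meets the second stop trigger. A mandatory action overrides a permissive one, so the reduction step is never used.

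**Step 3. Outcome for three kinds of patient.**

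| Patient on NB | Default and reduction sentences | Stop sentence, literal | Graded reading |
|---|---|---|---|
| Tolerable nausea | Continue | Stop | Continue |
| Intolerable effect, eases on a lower dose | May reduce | Stop | Reduce |
| Intolerable effect despite a lower dose | Silent | Stop | Stop |

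The readings differ in the first two rows. Putting reduction before stopping explains the trigger for patients who cannot tolerate the drug (row 3). It leaves the separate adverse-effects trigger unexplained.

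**Step 4. Does the vocabulary separate mild from grave effects?** Section 6.1.1 lists eight common *adverse reactions*: nausea, constipation, headache, vomiting, dizziness, insomnia, dry mouth and diarrhea. Section 3.3.1 lists *side effects* in two groups. "NB was associated with the following side effects in 10% or more of the time" introduces four: nausea, headache, constipation and vomiting. "NB was associated with the following side effects less than 10% of cases" introduces four more: dizziness, insomnia, dry mouth and diarrhea. That is 4 + 4 = 8, and all 8 of 8 appear in both lists. The plan does not reserve *adverse reactions* for graver events.

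**Step 5. Section 3.3.1.** Its closing sentence has two alternatives, and the severity qualifier attaches only to the second. The first, experiencing adverse reactions, is unqualified. Read literally, it also covers the significant effects that the same paragraph sends for a case-by-case decision.

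**Step 6. Does another section supply the missing limit?** The section 7.12 grades are not tied to any dosing action, and no other section states the order reduce, then stop.

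**Step 7. Can the effect be sized?** No. N is 25, but the number who will receive NB is not stated and could be anything from 0 to 25. The reaction rates in section 6.1.1 (7.1% for diarrhea to 32.5% for nausea) are for the marketed combination. The trials cited there used 32/360 mg per day in sustained-release form. This study gives 50/300 mg per day with immediate-release bupropion after bariatric surgery, so its rates may be lower or higher. A patient count would rest on assumptions for both inputs.

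**The case against.** The strongest reply is that nobody would read section 6.1.2 that way. The literal reading empties the sentence before it and makes the could-not-tolerate trigger redundant, whereas the sentence order gives each step work to do: continue, reduce, stop. This largely stands as evidence of intent, and the physician visits for reviewing side effects point the same way. It does not cure the text, because the unqualified trigger remains and is mandatory. Since section 6.2 actively asks about common NB effects, the question will come up in practice.

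A reader might infer that section 3.3.1 mandates stopping for any adverse effect and flatly contradicts itself. The documents do not support so strong a claim. Its closing sentence also contains a severity threshold, which implies that milder side effects do not stop NB. Its consultation step follows the suicidality questions and may be an escalation route for research clinicians rather than a competing dosing rule. What stands is that the unqualified alternative sits badly with the rest of the paragraph.

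A reader might also infer that the weight-loss interval is biased or that stops would go unseen. Neither follows. The interval still describes the non-responder arm as managed. The adverse-effect trigger ends the drug, not participation, and weight is still scheduled monthly. Pill counts, monthly adverse-event and compliance records and the examination of attrition (sections 6.2, 6.3.1 and 6.3.7) would show part of what happened. The plan does not say how a physician-directed stop counts in pill-count compliance, so no direction of effect on that outcome can be claimed.

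Finally, a low stopping threshold is defensible in an open-label pilot rated above minimal risk, with drug absorption possibly altered by surgery. If that is the intention, the dose-reduction sentence should go. As written, the section asks for both.

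**Conclusion.** Wrong as written, minor. Section 6.1.2 contains a mandatory, unqualified stopping trigger that, taken literally, leaves dose reduction without use and ends NB for tolerable common effects. Section 3.3.1 carries a similar but weaker inconsistency. A graded sequence is probably what was meant, so this is a drafting error in a dosing rule, not a statistical error.

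The conclusion rests on the wording and on one assumption: that an intolerable side effect counts as an adverse effect, which the 8-of-8 overlap of terms supports. It does not depend on any reaction rate. The effect on NB exposure, compliance or weight loss cannot be sized from the documents.

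**What to change.** Amend the stopping sentences in sections 6.1.2 and 3.3.1 to one graded rule:

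- Keep the planned dose while effects are tolerable.
- Where effects are intolerable, the physician may reduce the dose.
- Stop NB for adverse effects only if they remain intolerable despite reduction, or are serious or clinically significant in the study physician's judgement.
- Keep the existing stops for more than 7 consecutive days of non-compliance (6.1.2), emergent suicidality (6.1.1) and pregnancy (6.2.2). Leave the removal criteria in section 6.3.7 unchanged.
- Record the action and the reason for each dose reduction or stop.

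No automatic stop is proposed for seizure, liver dysfunction or glaucoma. Section 6.1.1 lists these as warnings without a stopping instruction, and the serious-or-clinically-significant criterion covers them.

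The cost is a short amendment to two sentences and one case-report field, with no extra visits or staff. The downside is that some patients with mild effects stay on NB under physician judgement, which has to be documented at visits planned to last only 10 to 15 minutes.
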